## **19 DATA AND RECORD KEEPING**

### ***19.1 Case Report Forms***

All data will be captured on 3-part carbonless paper and will be entered by the site staff and all queries will be addressed via PDF forms sent to sites via e-mail for resolution and sign-off. Cognition's data management team will employ double data entry. Standard procedures (including following data review guidelines, manual clinical review based on participant profiles, computerized validation to produce queries, and maintenance of an audit file which includes all database modifications) will be followed to ensure accurate data. Clinical personnel will review all data listings for outliers, data inconsistencies, and spelling errors.

During the course of the study, a study monitor (Clinical Research Associate) will make site visits to review protocol compliance, and review individual participant's medical records, assess drug accountability, and ensure that the study is being conducted according to pertinent regulatory requirements.

The review of medical records will be performed in a manner to ensure that participant confidentiality is maintained. Checking source documents is required to monitor the progress of the study. Direct access to source data is also required for inspections and audits, and will be carried out giving due consideration to data protection and medical confidentiality.

### ***19.2 Record Keeping***

Study records and source documents need to be preserved for at least 15 years after the completion or discontinuation of/withdrawal from the study or 2 years after the last approval of a marketing application of CT1812 in an ICH region, whichever is the longest time period. The sponsor will be notified prior to the planned destruction of any study related source documents.

## **20 FINANCING AND INSURANCE**

Financial aspects of the study are addressed in a separate clinical study agreement.

The Investigator is required to have adequate current insurance to cover claims for negligence and/or malpractice. The Sponsor will provide insurance coverage for the clinical study as required by national regulations.

## **21 USE OF DATA AND PUBLICATION POLICY**

Both the use of data and the publication policy are detailed within the clinical study agreement.

The Investigator should be aware that intellectual property rights (and related matters) generated by the Investigator and others performing the clinical study will be participant to the terms of a clinical study agreement that will be agreed between the Institution and the Sponsor or their designee. With respect to such rights, the Sponsor or their designee will solely own all right and interest in any materials, data and intellectual property rights developed by the Investigator and others performing the clinical study described in this protocol, participant to the terms of any such agreement. In order to facilitate such ownership, the Investigator will be required to assign all such inventions either to the Institution where the study is conducted or directly to the Sponsor or their designee, as will be set forth in the clinical study agreement. This agreement will not preclude the reporting of any required data to Regulatory Authorities.

## **23 APPENDICES**

Appendix A – Prohibited Medications

Appendix B - Prohibited Medications - Cytochrome P450 Drug Interaction Table

## Appendix A – Prohibited Medications

Use of below restricted medications within 4 weeks of screening visit and during the course of the study. Exceptions to the list of excluded medications may be made on a case-by-case basis if discussed and approved by the medical monitor in advance.

- Antipsychotic agents (except risperidone  $\leq 1.5$  mg/day, quetiapine  $\leq 100$  mg/day, olanzapine  $\leq 5$  mg/day, and aripiprazole  $\leq 10$  mg/day)
- Antiepileptics (except lamotrigine, gabapentin and pregabalin for nonseizure indications))
- Centrally active anti-hypertensive drugs (e.g., clonidine, l-methyl dopa, guanidine, guanfacine, etc.)
- Sedatives or anxiolytics; use of short- to medium-acting benzodiazepines for treatment of insomnia is permitted, however, use of sedatives or hypnotics should be avoided for 8 hours before administration of cognitive tests.
  - Low dose lorazepam may be used for sedation prior to MRI scan for those patients requiring sedation. At the discretion of the investigator, 0.5 to 1 mg may be given orally prior to scan with a single repeat dose given if the first dose is ineffective. No more than a total of 2 mg lorazepam may be used for the MRI scan.
- Opiate analgesics
- Systemic corticosteroids
- Mood stabilizers (e.g., valproate, lithium);
- Moderate to strong inhibitors or inducers of CYP3A4. See Appendix B for a complete list of restricted medications.
- All hormonal contraceptives and hormone replacement therapies (oral, injectable, transdermal or implanted)
- Calcium channel blockers (verapamil and diltiazem)
- Calcium supplements greater than 1300 mg per day
- Furosemide (Lasix®)
- Coumadin®
- Digoxin

Inability to separate dosing by at least 6 hours (before or after) of CT1812 from participant medications which are sensitive or narrow therapeutic index substrates of CYP3A4, or substrates of P-gp, e.g., loperamide, vinblastine or talinolol.

## Appendix B – Prohibited Medications - Cytochrome P450 Drug Interaction Table

In addition to the medications detailed in Section 9.3 (Exclusion Criteria) the following are prohibited for 4 weeks prior to screening and for the duration of the study due to interactions with cytochrome P450 or P-gp.

3A4,5,7 INHIBITORS	3A4,5,7 INDUCERS
HIV Antivirals: indinavir nelfinavir ritonavir  clarithromycin itraconazole ketoconazole nefazodone erythromycin grapefruit juice verapamil  suboxone diltiazem	Carbamazepine efavirenz nevaripine phenobarbital phenytoin pioglitazone rifabutin rifampin St. John's Wort troglitazone

---

### **Sensitive P-gp Substrate**

Digoxin

*From: Flockhart DA. Drug Interactions: Cytochrome P450 Drug Interaction Table. Indiana University School of Medicine (2007).* [REDACTED]

[REDACTED]

1. SCOPE OF THE STATISTICAL ANALYSIS PLAN

This Statistical Analysis Plan is an adjunct to Cognition Therapeutics, Inc. Protocol No. COG0105 dated 03 February 2021, Version 1.5. The Statistical Analysis Plan details the pre-planned procedures for the pharmacokinetic and statistical methods used in the analysis of the clinical data.

Additional analyses may be explored as well upon review of the unblinded results and will be considered as post hoc analyses.

2. ABBREVIATIONS

AD	Alzheimer’s disease
ADAS-Cog	Alzheimer’s Disease Assessment Scale – cognition subscale
ADCS-ADL	Alzheimer’s Disease Cooperative Study – Activities of Daily Living
ADCS-CGIC	Alzheimer’s Disease Cooperative Study – Clinical Global Impression of Change
AE	Adverse event
ANCOVA	Analysis of covariance
BMI	Body mass index
CDR-SB	Clinical Dementia Rating Scale Sum of Boxes
CRF	Case report form
DVR	Distribution volume ratio
ECG	Electrocardiogram
fMRI	functional magnetic resonance imaging
GDS	Geriatric Depression Scale
ICC	Intrinsic Connectivity Contrast
ICH	International Council for Harmonisation of Technical Requirements for Pharmaceuticals for Human Use
IP	Investigational Product
MedDRA	Medical Dictionary for Regulatory Activities
MMSE	Mini Mental State Exam
NTB	Neuropsychological Test Battery
PD	Pharmacodynamic
PK	Pharmacokinetic
QA	Quality assurance
QC	Quality control
SAE	Serious adverse event

SAP	Statistical analysis plan
SMC	Safety monitoring committee
SOP	Standard operating procedure
SUVR	SUV ratio
WHODrug	WHO Drug Dictionary

3. RELEVANT AVANCE STANDARD OPERATING PROCEDURES AND GUIDANCES

The following Avance SOPs and regulatory guidances are relevant to this Statistical Analysis Plan:

- SOP BIOM-0002 Clinical Data Analysis and Presentation
- SOP BIOM-0003 Blinding: Codes and Code Breaking
- SOP BIOM-0004 Randomisation Generation
- SOP BIOM-0007 Pharmacokinetic Analysis Using WinNonlin
- SOP BIOM-0009 Statistical Analysis Plans
- ICH: Statistical Principles for Clinical Trials (ICH E9, Current Step 4 version dated 5 February 1998)
- FDA: Bioavailability and Bioequivalence Studies for Orally Administered Drug Products – General Considerations (Revision 1, March 2003).
- Bioavailability Studies Submitted in NDAs or INDs – General Considerations (latest draft February 2019)

4. INTRODUCTION

4.1. Study Overview

This is a randomized, double-blind, placebo-controlled, parallel-group trial evaluating CT1812 with planned dose levels of 100 mg and 300 mg.

4.2. Study Objectives

Primary:

- To evaluate the safety and tolerability of CT1812 in AD patients

Secondary:

- To evaluate the effect of CT1812 on brain synaptic density in AD patients using the SV2A PET ligand ¹¹C-UCB-J.
- To evaluate the effect of CT1812 on cognitive and clinical outcomes in AD patients using the ADAS-COG, NTB, derived cognitive composites, ADCS-ADL, MMSE, CDR-SB, and ADCS-CGIC

- To evaluate the effect of CT1812 on brain activity in AD patients using FDG PET, resting state functional MRI
- To evaluate the effect of CT1812 on brain volume in AD patients using volumetric MRI
- To evaluate the effect of CT1812 on CSF pharmacodynamics in AD patients through measurement of CSF A β 40, A β 42, tau, phospho-tau, neurogranin, synaptosomal-associated protein-25 (SNAP25), synaptotagmin, and NFL. Additional CSF biomarkers are listed in Section 11.5.
- To evaluate the plasma and CSF concentrations of CT1812 in AD patients.

Exploratory:

- To correlate changes in synaptic density, other imaging endpoints and biomarkers, with cognitive function following CT1812 treatment.
- To evaluate the plasma CT1812 metabolites in AD patients

4.3. Study Design

This is a single-center, Phase 1b, randomized, double-blind, placebo-controlled, parallel-group trial in adults with mild to moderate AD.

After consenting to participate in the study, screening procedures will occur between Days -60 and -1. Eligible participants will be randomized in a 1:1:1 (300 mg active: 100 mg active: placebo) ratio. The first dose of study drug will be administered in the clinic after all baseline procedures have been conducted. For the remainder of study days, participants will ingest study drug each morning at home. Participants and their study partners will return to the clinic for repeat psychometric/neurologic testing, safety studies, and PK and PD sample collection approximately every 2 weeks for the first 6 weeks and then every 3 weeks thereafter up to 24 weeks for the primary study followed by an optional double-blind extension treatment period of an additional 24 weeks (337 days +/-2) as well as a follow up visit at 2 weeks after the final treatment visit

Participants who prematurely discontinue the study for any reason will be asked to attend a final safety and efficacy visit.

4.4. Study Treatment

CT1812 will be provided as a hydroxypropyl methylcellulose (HPMC) capsule containing 191 mg or 64 mg of CT1812 fumarate salt (equivalent to 150 mg or 50 mg of the CT1812 free base, respectively).

Placebo capsules (containing of 191 mg or 64 mg of lactose monohydrate) will be supplied to match the CT1812 supplies in the same packaging.

CT1812 or matching placebo will be administered once each morning as a 300 mg or 100 mg oral dose (2 capsules).

4.5. Sample Size

Computation of sample size in this within-participant design was based on estimates of the magnitude of reductions in synaptic density from post-mortem AD data of 25-45%. It

was assumed that, on average, there is 30% loss of synapses in this population, and that CT1812 would restore one third of those synapses, with no change in synaptic density in the placebo group. Based on the excellent test/retest reliability of ^{11}C UCB J, it was conservatively assumed 10% variability in baseline and post-treatment ^{11}C UCB J binding potential non-displaceable (BPND) measurements. Power was first computed by assessing whether the change in synaptic density would be larger in the treated group than the placebo group.

For group sizes of 7 per group, one has ~68% power for comparison of the combined treatment of N=14 CT1812 vs. 7 placebo subjects ($\alpha = 0.05$, 1-tailed test). Higher power was present in the one-sample test of the treatment group, i.e., did synaptic density increase following CT1812 treatment. In that case, a group size of 7 CT1812 patients yields 80% power to detect an increase in synaptic density. Power for detecting changes in 18F FDG is likely to be lower since the magnitude of change in the SV2A signal in AD will be larger than that of 18F FDG (20%).

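### The stated 80% power for the one-sample test with 7 CT1812 patients looks like a known-variance normal figure; a t-test on the same apparent inputs gives about 71% to 76%

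*SAP*

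**What the plan says.** SAP section 4.5 and Protocol section 17.5 give the same calculation. The assumptions, in the SAP's words, are that "on average, there is 30% loss of synapses in this population", that "CT1812 would restore one third of those synapses, with no change in synaptic density in the placebo group", and, for the PET measurements, "it was conservatively assumed 10% variability in baseline and post-treatment".

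Two powers follow. The first is for drug against placebo: "For group sizes of 7 per group, one has ~68% power for comparison of the combined treatment of N=14 CT1812 vs. 7 placebo subjects", at a one-tailed 5% level. The second is for change within treated patients. The SAP introduces it with "Higher power was present in the one-sample test of the treatment group, i.e., did synaptic density increase following CT1812 treatment" and concludes that "a group size of 7 CT1812 patients yields 80% power to detect an increase in synaptic density".

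Neither document says whether the reference distribution is normal or t. Neither gives the SD of the change, the scale on which the 10% is measured, or a correlation between the two scans.

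**The concern.** At n = 7 the choice between a normal and a t calculation matters. The normal formula takes the SD of change as known, whereas a one-sample test on 7 patients estimates it on 6 degrees of freedom and uses a critical value of 1.943 instead of 1.645. If the printed 80% came from the normal formula, it overstates the power of the test that the SAP names.

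The 80% is the only power in either document at a conventional level. A null SV2A result would be read partly against it. On the readings below, the chance of missing the assumed effect in the one-sample test is 24% to 29%, not 20%.

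This point keeps the plan's own tests, direction and alpha. It concerns only how the power was computed.

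**Working it through.** **Inputs (SAP 4.5, Protocol 17.5), on a scale with healthy = 100**
- Baseline mean: 100 − 30 = 70.
- Treated mean after treatment: 70 + 30/3 = 80, so the effect is 10. Placebo change is 0.
- Alpha: 5%, one-tailed. The label is attached to the two-sample comparison. The one-sample question is directional in its wording, so it is taken as one-tailed too.
- Group sizes: 7 for the one-sample test; 14 versus 7 for the comparison.

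**Assumed here, because the documents do not say**
- Reading A: the SD at each scan is 10% of the current level (7 at a mean of 70, 8 at a mean of 80), with independent errors.
  - SD of change, treated: √(7² + 8²) = √113 = 10.63.
  - SD of change, placebo: √(7² + 7²) = √98 = 9.90.
- Reading B: the SD is 10% of baseline at both scans (7 and 7), with independent errors. SD of change in both arms: √98 = 9.90.

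**Step 1. Reproduce the printed figures with the normal formula, reading A**
- One-sample: Φ(10/(10.63/√7) − 1.645) = Φ(2.489 − 1.645) = Φ(0.844) = 80.1%. Printed: 80%.
- 14 versus 7: Φ(10/√(113/14 + 98/7) − 1.645) = Φ(10/4.698 − 1.645) = Φ(0.484) = 68.6%. Printed: about 68%.

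Reading B with the normal formula gives 84.8% and 70.4%. Taking 10 points of normal as the SD at each scan gives 58.9% and 45.3%. A log-ratio scale gives 80.3% and 65.4%. Of the variants tried, only reading A with the normal formula returns both printed values.

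**Step 2. Same tests, same inputs, SD estimated**
- Reading A, one-sample: noncentral t, 6 df, noncentrality 2.489: 70.9%.
- Reading A, 14 versus 7: about 64% (64.2% in 400,000 simulated trials, for both the pooled-variance and the Welch test; the noncentral-t approximations are 63.9% and 64.5%).
- Reading B, one-sample: noncentrality 10/(9.90/√7) = 2.673, 6 df: 76.2%.
- Reading B, 14 versus 7: noncentrality 10/(9.90·√(1/14 + 1/7)) = 2.182, 19 df: 67.7% (Welch 66.0%).

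| Test | Printed | Normal, A | t, A | t, B |
|---|---|---|---|---|
| One-sample, n = 7 | 80% | 80.1% | 70.9% | 76.2% |
| 14 vs 7 | ~68% | 68.6% | about 64% | 67.7% |

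**Step 3. What 80% would require.** A one-tailed one-sample t-test with 7 patients reaches 80% at a standardised effect of about 1.07. Reading A gives 10/10.63 = 0.94 and reading B gives 10/9.90 = 1.01.

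**Step 4. Sensitivity to correlated scans.** With SDs of 7 and 7 and a correlation of 0.10, the SD of change is √(98 × 0.9) = 9.39 and the one-sample t-test on 6 df has 79.9% power. The same assumption gives 71.6% for 14 versus 7, so it does not return the printed pair.

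**The case against.** The strongest reply is that the SD of change is inferred. The values 10.63 and 9.90 were chosen because they reproduce the printed pair, and the sponsor may have used something else. That stands: they should be treated as an assumption, not as the sponsor's input.

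It follows that a reader should not infer that no t-based calculation can give 80% with 7 patients. A scan correlation of 0.10 with SDs of 7 and 7 does so (step 4). So, roughly, does testing one arm's mean change against the residual of a three-arm model on 21 − 3 = 18 df: 82.3% with SDs of 7 and 7, next to 67.7% for 14 versus 7. However, SAP 4.5 states no correlation and names a one-sample test, and SAP sections 9.3 and 10 describe comparisons with placebo, not a within-arm test of this kind.

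Nor should a reader infer that both printed figures are wrong. Under reading B the pooled figure is 67.7%, which rounds to the printed value.

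Finally, the consequence is limited. The trial is a pilot with safety as its primary objective, the imaging endpoint is secondary and defined against placebo, and the sections put the drug-versus-placebo power first. All of that stands, and it argues for a correction of wording and no more.

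**Conclusion.** The one-sample 80% is not supported as written. On the two natural readings of the stated inputs, with independent scan errors, the t-test power with 7 patients is 71% to 76%, so the printed figure is about 4 to 9 points too high. That the normal formula under reading A returns both printed values is good evidence of how they arose, but not proof.

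The figure of about 68% for 14 versus 7 is 0 to 4 points too high and may be essentially correct.

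The result rests on independent scan errors, on 10% being an SD relative to the current or the baseline level, and on a one-tailed one-sample test. A positive correlation would raise the power. A two-sided one-sample test would lower it, to 55.0% under reading A.

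Nothing here shows that the sample size must change. For scale only, a one-sample t-test first passes 80% at n = 9 under reading A (82.3%; n = 8 gives 77.3%) and at n = 8 under reading B (82%).

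**What to change.** In SAP section 4.5 and Protocol section 17.5:
- State the SD of change and the scan-to-scan correlation that were actually assumed, with the scale of the 10% and the formula used.
- Replace the normal-formula figures with noncentral-t values for the same one-tailed tests. Under independent errors these are about 71% (range 71% to 76%) for the one-sample test with 7, and about 64% (range 64% to 68%) for 14 versus 7.
- If a positive correlation was assumed, state it and recompute both figures.

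The cost is wording in two sections and a less favourable stated power. No sample size, test, visit or analysis changes.

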4.6. Study Endpoints

Safety Endpoints:

- The incidence and severity of adverse events (AE)
- The incidence of serious adverse events (SAE)
- Changes in vital signs
- Changes in physical and neurological exam findings
- Changes in body mass
- Changes in electrocardiogram (ECG) findings
- Changes in clinical laboratory testing (serum chemistry, hematology, urinalysis)
- Changes in the Columbia Suicide Severity Rating Scale (C-SSRS)

Secondary:

- The primary imaging endpoint is the change from the baseline in synaptic density as measured by differences in SV2A PET ligand ^{11}C -UCB-J uptake after dosing with CT1812 versus placebo.
- Cognitive and clinical outcomes:
 - Mini Mental State Exam (MMSE).
 - Alzheimer's Disease Assessment Scale-Cognitive Subscale (ADAS-Cog) 11 and ADAS-Cog13 (delayed recall and Number Cancellation added to ADAS-Cog11 in the ADAS-Cog13); ADAS-Cog14 includes the maze added to ADAS-Cog13.
 - Neuropsychological Test Battery (NTB) including Trails A and B, Digit Span, and Letter and Category Fluency (CFT).
 - Alzheimer's Disease Cooperative Study (ADCS)-Clinical Global Impression of Change (CGIC).

- ADCS-Activities of Daily Living (ADCS-ADL).
- Clinical Dementia Rating Scale – Sum of Boxes (CDR-SB)
- Composite z-score scales (Cognitive Composite score; Memory composite score; Attention composite score; Executive Function composite score).
- CSF pharmacodynamics in AD patients through measurement of CSF A β 40, A β 42, tau, phospho-tau, neurogranin, synaptotagmin, SNAP25, and NFL.
- Imaging Outcomes
 - FDG PET
 - Functional MRI
 - Volumetric MRI

Pharmacokinetic Endpoints:

- The following CT1812 pharmacokinetic assessments will be made based on serial pre-dose concentrations in plasma and CSF:
 - CT1812 CSF/plasma concentration ratio
 - Changes in pre-dose CT1812 plasma concentrations
 - Plasma CT1812 metabolites

5. DATA LISTINGS

5.1. Sources of Data

Data sets containing raw data will be provided by the Data Management group, extracted from the clinical study database of data entered into a Case Report Form. It is assumed that the database will contain the data from Screening through to the Follow-up Safety Visit of the study.

Analysis datasets will be generated from the data extracted from the study database, along with the following data entered separately or received from other sources:

- Randomisation/treatment assignment data, to be provided by the Avance unblinded statisticians
- Clinical laboratory safety data, to be provided by Quest Diagnostics to Avance Clinical data management
- CSF and plasma PK concentration data, to be provided by Agilex Biolabs
- PD concentration data (CSF) data, to be provided by Agilex Biolabs

All data entered into the CRF or provided from other sources as described above will be presented (explicitly or implicitly) in data listings or figures as described in Appendix 1. All available data collected for screen failed individuals will also be included in the individual data listings.

5.2. Randomization and Subject Identification Code

This is a double-blind, placebo-controlled study. Study drug will consist of either of two doses of CT1812 or placebo. The placebo will be identical in appearance to both doses of the active CT1812.

The non-blinded statistician assigned to the trial will generate a list with the appropriate number of 4 digit individual study IDs randomly for each arm, randomly assigned to either CT1812 300 mg, CT1812 100 mg or placebo treatment in a 1:1:1 ratio. Randomization will include a stratification factor for the MMSE score (18-22 or 23-26).

The Randomisation Number will be specified as Rrnnn, where:

- nnn = sequential subject id from 001 to 999,

In the listings presenting the individual data, subjects will be identified by randomization number, with dose of CT1812 as a secondary grouping identifier. The screening number will be shown only on the listing of informed consent data.

